6.10.4 Statistical Methods

6.10.4.1 Statistical Analysis Plan:

Study data will be analysed at three time points:

- At the end of the stage 1 screening study, demographic, clinical chemistry and haemodynamic study data will be analysed in a cross-sectional analysis.
- After the initial cMRI, the STOP/GO checkpoint analysis will be performed and cMRI data will be analysed together with stage 1 study data in cross-sectional analyses.
- At the end of the stage 2 RCT and observational follow-up study primary, secondary and other endpoints will be analysed and a longitudinal data analysis will be performed.

6.10.4.2 Statistical Methods – Outcomes:

STAGE 1: Central aortic systolic pressure (CASP) distribution will be used to stratify participants as potential candidates for stage 2. Participants with CASP values above the 75th percentile will be candidates for randomisation into the trial. Simple, unrestricted randomisation will be used. Those with CASP less than the 25th percentile will be offered participation in the observational follow-up part of stage 2.

STAGE 2: All analyses for outcomes in the RCT will be carried out on the basis of the originally assigned groups, whether participants complete treatment or not as per CONSORT guidelines ⁽⁸⁷⁾. Multilevel mixed-effects linear regression models with a maximum likelihood estimator will be used and will account for the repeated measures nature of the data. These models are inherently robust to missing data, dealing with missing values in a similar manner to multiple imputation approaches.

The principal outcome for assessment will be change in LV mass index over the 1-year follow-up period. This will be compared between the two groups without adjustment and then with adjustment for potential confounders in multivariable models. Such additional variables will include, but not be limited to, age, brachial artery systolic pressure, smoking history and measures of adiposity such as BMI. Over-fitting of models will be avoided by careful attention to the adjusted r²

of the models. Thus, only coefficients that significantly improve the fit of the models or where a strong case for their known biological importance can be made will be included. Results will be presented in a multi-stage format so that readers can assess the unadjusted and adjusted models separately. Where predictor variables are suspected to have a non-linear influence on outcome (e.g. on LV mass index), further polynomial terms may be added (e.g. quadratic and cubic) but careful examination of model fits to raw data will be made to prevent such models from over-fitting the data in a spurious sense. Where interactions between predictor variables are suspected on the basis of biological plausibility e.g. varying influence of adiposity on LV mass index with age, the appropriate interaction terms will be added to the models to assess this. Outliers will be dealt with on a case-by-case basis and excluded if values are biologically implausible or can be found to be erroneous after reference to the raw data.

No interim analyses will be performed in accordance with the blinded nature of the study. Results will be reported as per CONSORT guidelines ⁽⁸⁷⁾.

6.10.4.2.1 Data Manipulation:

In all cases, parametric analyses will be preferred and applied to data with normal distributions or after appropriate transformation to normality e.g. Log transformation for right-skewed data.

6.10.4.2.2 Missing Data:

For missing data appropriate procedures will be used such as multiple imputation procedures or (where y-values are (MAR) missing at random), the bootstrap approach as suggested by Efron ⁽⁸⁶⁾.

6.10.4.2.3 Analysis of the STOP/GO Checkpoint:

It is a STOP/GO condition of the study prior to stage 2 that the high and low CASP groups must have a significant (P<0.05) difference in LV mass index. Student t-test comparison of the groups will be used to assess this.

6.10.4.2.4 Economic evaluations:

No economic evaluations are planned. Evaluation of cost effectiveness of the study medications in terms of quality adjusted life years (QALYs) is well established ⁽⁴⁾.

6.10.4.2.5 Additional Analyses – Subgroup:

No additional analysis in sub-groups is planned.

6.10.4.2.6 Additional Analyses - Adjusted:

No additional analysis in sub-groups is planned.

6.10.4.2.7 Analysis Population and Missing Data:

The analysis population and strategies for dealing with missing data are outlined in section 6.10.4.2 – statistical methods.

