6.3.1.8 Defining the LOW CASP and HIGH CASP Groups - Stratification According CASP

After 500 participants have been recruited into the stage 1 screening study, data from participants will be stratified according to their CASP values. Based on the distribution of CASP values from our previous studies, we will select the upper 25% of CASP values to define the HIGH CASP group (n=130) who will be invited to participate in the RCT if the study progresses to the second stage. We will also select 65 participants with the lowest CASP values who will form the LOW CASP observational cohort and will be invited to participate in the observational follow-up study. Our preliminary data suggests that stratifying the stage 1 study population in this manner will result in an upper limit CASP value for the LOW CASP group of 129mmHg, and lower limit value for the HIGH CASP groups. We recognise that this will most likely generate two groups with different brachial BP values as well different CASP values. However, according to current guidance, treatment would not be offered on the basis of the brachial BP value alone. Furthermore, CASP cannot be predicted from the brachial BP and we are specifically evaluating the use of CASP to stratify the patients for treatment.

We plan to screen up to 500 participants in Stage 1 of the study, however, as screening proceeds, the distribution of CASP values will be monitored and modelled by the study statistician. It is possible that fewer people will need to be screened to identify the required number of participants for the LOW CASP and HIGH CASP cohorts with the desired CASP separation.

Once identified, people in the HIGH CASP (n=130) and the LOW (n=65) groups will be invited to return to the research unit to undergo cardiac MRI for detailed evaluation of left ventricular mass index (LVMI) and cardiac and vascular structure and function. This evaluation will dictate whether the TREAT CASP study progresses to the stage 2 randomised clinical trial and observational follow-up study.

6.3.1.9 STOP/GO Checkpoint:

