A STOP/GO checkpoint has been incorporated into the study design which will be evaluated before the study proceeds to the second stage. The STOP/GO checkpoint will be implemented to avoid futility in implementing the second part of the study i.e. if there is no difference in cardiac structure between the HIGH and LOW CASP cohorts there would be little likely benefit in stratifying participants by their central BP for subsequent treatment for blood pressure lowering.

Cardiac MRI (cMRI) will be used to measure left ventricular mass index in participants from the HIGH and LOW CASP groups participating in the stage 1 screening study. This data will be used to evaluate

the STOP/GO checkpoint. If a difference in LVMI is observed between participants from the HIGH and LOW CASP groups, the null hypothesis that there is no difference in LVMI between groups will be rejected and the study can proceed to the second stage. If the null hypothesis is not rejected i.e. if there is no difference in LVMI between people from the HIGH and LOW CASP groups, the TREAT CASP study will be terminated at this point. This evaluation will be used to confirm or refute the first key element of our hypothesis, i.e. whether CASP has been effective at identifying patients with and without pressure-related target organ damage, irrespective of their brachial blood pressure values.

The decision to proceed to the second stage of the study will be taken by the Trial Steering Committee. The data upon which the STOP/GO decision is made will be reviewed by an independent statistician who will provide recommendations to the Trial Steering Committee.

6.3.1.10 STAGE 2 Randomised Clinical Trial and Observational Follow-up Study:

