The inbuilt STOP/GO checkpoint to allow the study to proceed to the RCT (stage 2) is based on achieving a significant difference in LVMI as measured by MRI between people in the HIGH CASP and LOW CASP groups at the end of the screening phase (stage 1 see section 6.3.1.7).

Previously published studies indicate that LVMI is directly related to blood pressure and that the relationship between the change in systolic blood pressure and the change in LVMI approximates to the order of $1g/m^2$ LVMI per mmHg SBP ^(57,58). This order of magnitude of change is similar to that seen for the regression in LVMI with BP-lowering treatment in the analysis of published studies for the RCT power calculation (average reduction in SBP -8 mmHg, average reduction in LVMI with treatment -6.6 g/ m^2). Preliminary data from our clinical laboratory in men with stage 1 hypertension stratified by their CASP values indicates that groups incorporating the highest and lowest 25% of the population with regard to their CASP values are separated by brachial systolic blood pressures of at least 10mmHg [Appendix, figure 7]. Based on the relationship between LVMI and BP as outlined above, this indicates a likely separation between groups in LVMI of approximately $10g/m^2$. With regard to a starting value, systematic review of LVMI values by MRI in 1,032 young men from 11 published studies indicates a mean value of 78.5 g/m², SD 11.8g/m² ($^{59-67}$). Combining an estimated 10g/m² difference between the HIGH and LOW CASP groups with the SD for LVMI in young men, indicates a sample size of 31 per group would be required to demonstrate a difference in LVMI with 90% power at p=0.05. This indicates that a sample size of 65 individuals in the LOW CASP and 130 individuals for the HIGH CASP group should have abundant power to demonstrate a difference in LVMI at the study STOP/GO checkpoint. This will provide a robust basis to confirm or refute our hypothesis that CASP provides an effective mechanism for identifying patients with and without pressure-related target organ damage, in people with a diagnosis of stage 1 hypertension.

6.7.2.1 Consideration of variability in LVMI:

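### The STOP/GO t-test cannot separate CASP from brachial pressure, so it cannot support the conclusion that CASP identifies damage irrespective of brachial BP

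*Protocol*

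**What the plan says.** Section 6.10.4.2.3 fixes the rule: "the high and low CASP groups must have a significant (P<0.05) difference in LV mass index", and "Student t-test comparison of the groups will be used to assess this". It names no covariate, direction or minimum difference.

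Section 6.3.1.9 gives the purpose: "The STOP/GO checkpoint will be implemented to avoid futility in implementing the second part of the study". It also attaches an inference. The evaluation is to confirm or refute whether "CASP has been effective at identifying patients with and without pressure-related target organ damage, irrespective of their brachial blood pressure values".

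Two other sections bear on that inference. Section 6.3.1.8 concedes that selecting on CASP means "this will most likely generate two groups with different brachial BP values as well different CASP values". Section 6.7.2 sizes the checkpoint from preliminary data in which the top and bottom quarters by CASP "are separated by brachial systolic blood pressures of at least 10mmHg". It multiplies that gap by about 1 g/m² of LVMI per mmHg of SBP to reach 10 g/m², and this "indicates a sample size of 31 per group would be required to demonstrate a difference in LVMI with 90% power at p=0.05". The groups will in fact hold 130 and 65 men.

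**The concern.** The rival explanation for any HIGH-LOW difference in LVMI is brachial pressure, and the checkpoint is sized on that explanation. If LVMI followed brachial SBP exactly as section 6.7.2 assumes and CASP added nothing, the expected difference would still be the 10 g/m² the test is designed to find. A GO would then be read as showing that CASP works irrespective of brachial BP, when the comparison holds nothing about brachial BP constant.

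This touches the trial's central question. Key research questions 1 and 3 (section 5.2.3) ask whether CASP adds to, or is more closely tied to early damage than, brachial pressure. Section 5.3 makes the decision to proceed depend on the first part of the hypothesis being proven. The randomised comparison and the primary outcome are not affected. What is at stake is the conclusion drawn from stage 1.

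**Working it through.** **Inputs.** From section 6.7.2: SD of LVMI 11.8 g/m²; brachial SBP gap at least 10 mmHg; slope about 1 g/m² per mmHg; groups of 130 and 65. From section 6.10.4.2.3: P<0.05, taken as two-sided because no direction is given. From section 6.7.1: RCT difference 6.6 g/m², SD 10.9 g/m², 58 per arm, 90% power.

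**The plan's own figure.** n per group = 2 × (1.960 + 1.282)² × (11.8/10)² = 29.3, so 30 by the normal approximation and 31 by the exact t calculation. The stated 31 is reproduced. The arithmetic is sound; the question is what the test can show.

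**Chance of GO if LVMI depends on brachial SBP alone.** SE = 11.8 × √(1/130 + 1/65) = 1.79 g/m². The critical value of t on 193 df is 1.972. The true difference is slope × 10 mmHg, and power comes from the non-central t distribution:

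| Slope (g/m² per mmHg) | Difference (g/m²) | P(GO), SD 11.8 | P(GO), SD 17.7 |
|---|---|---|---|
| 1.0 (section 6.7.2) | 10 | 99.98% | 95.9% |
| 0.825 (= 6.6/8, section 6.7.2) | 8.25 | 99.6% | 86.3% |
| 0.5 (assumed) | 5 | 79.3% | 45.6% |
| 0.3 (assumed) | 3 | 38.4% | 19.9% |

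The SD of 17.7 is the 50% increase considered in section 6.7.2.1 (11.8 × 1.5).

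**The same case with brachial adjustment.** A simulation screened 500 men, took the top 130 and bottom 65 by CASP, and let LVMI depend only on brachial SBP (1 g/m² per mmHg, residual SD 11.8, 10 mmHg separation). The documents give no CASP-brachial correlation, so 0.5, 0.7 and 0.9 were assumed. The planned t-test gave GO in 99.8% to 99.9% of runs. The CASP-group effect adjusted for brachial SBP averaged about 0 and was significant in 4.5% to 4.8%, close to its nominal 5%.

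**Precision of the adjusted effect.** Its SE is about 2.2 g/m² at a correlation of 0.5 and about 4.0 at 0.9, against 1.8 unadjusted. For 80% power the adjusted effect would have to be about 2.8 × SE, that is 2.8 × 2.2 = 6.2 to 2.8 × 4.0 = 11.2 g/m².

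**Smallest observed gap that gives GO.** 1.972 × 1.79 = 3.5 g/m². A true gap of 3.5 gives GO about 49% of the time, and a true gap of 2 about 20%.

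**Conditional RCT power.** With SD 10.9 and 58 per arm, SE = 10.9 × √(2/58) = 2.02 g/m². Power is about 90% at 6.6 g/m² and about 40% at 3.5 g/m². The second figure matters only if regression cannot exceed a HIGH-LOW gap of that size.

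**The case against.** The protocol does not leave CASP versus brachial BP to this t-test alone. Section 6.5.2 plans cross-sectional comparisons of the two pressures, section 6.10.4.1 analyses the first cMRI data together with the stage 1 data, and the models may properly sit in a SAP. GO is also not automatic: an independent statistician reviews the data and the Trial Steering Committee decides. All of this stands, but none of it changes the rule in section 6.10.4.2.3 or the inference that section 6.3.1.9 draws from it. Section 6.3.1.8 defends the brachial imbalance on the grounds that brachial BP alone would not trigger treatment and that CASP cannot be predicted from it. Neither removes a known imbalance from an unadjusted comparison of means.

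The adjusted analysis is itself limited. It is imprecise, and CASP is calibrated to the same cuff reading (section 6.10.1.2), so shared measurement error may leave residual bias. That stands, and is why it should not become the gate.

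A reader might also infer that the checkpoint fails its anti-futility purpose because a gap of 3.5 g/m² opens an RCT with 40% power. The documents do not support that. Section 6.3.1.9 describes futility as no difference in cardiac structure, which the t-test does address, and a true gap of 3.5 is stopped about half the time. The 40% needs a ceiling on regression that the protocol never states. Section 6.3.1.10 describes the damage as LVMI elevated relative to the LOW group, and section 6.4.8 uses that group as a reference; neither is a limit.

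The missing direction is a small matter. A significant result with HIGH below LOW has probability 2.5% when there is no true difference, and section 6.3.1.10 already implies the direction.

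**Conclusion.** The claim in section 6.3.1.9 about brachial pressure is wrong as written. An unadjusted comparison of groups expected to differ by at least 10 mmHg in brachial SBP cannot show that CASP works irrespective of it, at any slope. On the protocol's own slope, separation and SD, GO is about 99.98% likely even if CASP adds nothing. It would be an overstatement to say that GO is near certain in general: the figure falls to about 79% at 0.5 and 38% at 0.3 g/m² per mmHg. The adjusted results rest on assumed correlations, normal distributions and brachial SBP measured without error. The RCT power figure is secondary and conditional on the assumed ceiling. The fault lies in the interpretation of stage 1, not in the sample size arithmetic or the randomised comparison.

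**What to change.** 1. Keep the t-test as the gate in section 6.10.4.2.3, and state that GO requires HIGH above LOW, consistent with section 6.3.1.10.
2. In section 6.3.1.9, delete the reference to brachial pressure as a conclusion of that test.
3. Before the checkpoint is analysed, prespecify a linear regression of LVMI on CASP group adjusted for seated brachial SBP, age and BMI. Report the adjusted difference and its 95% CI to the Trial Steering Committee beside the t-test, as the evidence on the first hypothesis and not as a gate.
4. Optionally, if the observed gap is below 6.6 g/m², show the committee the RCT power with regression limited to that gap, labelled as a sensitivity figure. If the true gap is 10 g/m², this would be needed only about 3% of the time: (10 − 6.6)/1.79 = 1.90, so an observed gap of at least 6.6 occurs with probability 97%.

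The cost is one regression on data already collected at screening and the baseline cMRI, and a change of wording; no extra scans are needed. The downside is an adjusted estimate with an SE of about 2.2 to 4.0 g/m² and possible residual bias from the shared cuff calibration. The text should therefore say that a null adjusted result is not proof that CASP adds nothing.

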6.11 Data Monitoring

6.11.1 Independent Data Monitoring and Ethics Committee:

An independent Data Monitoring and Ethics Committee (DMEC) will be established for stage 2 of the study if the STOP/GO criteria are met and the study proceeds to stage 2. We do not anticipate any

major safety concerns with this study. The RCT in stage 2 is a single centre study, using established and licensed medications for one year duration. The DMEC will be independent of the TSC. There will be no planned interim analysis of the 12 month RCT and the role of the DMEC will be to assess safety reports and make recommendations to the TSC.

Further details of the roles and responsibilities of the Data Monitoring and Ethics Committee (DMEC) including membership, relationships with other committees, decision making processes, and the timing and frequency of interim analyses (and description of stopping rules and/or guidelines where applicable) are described in detail in the TREAT CASP study DMEC Terms of Reference (ToR).

6.11.2 Interim Analyses

No interim analyses are planned.

6.11.3 Data Monitoring for Harm

This is a not a clinical trial of an Investigational Medicinal Products and treatments used in this study have well known safety profiles. Nevertheless, data on adverse events will be collected by the research nurse at routine study visits. Adverse events inconsistent with the known effects of study medication will be reported via the yellow card system through the MHRA website ⁽⁸⁷⁾ at the judgement of the study physician and CI This data will be reported to the UCL CTU at the same time.

6.11.3.1 Safety reporting:

Definitions of harm of the EU Directive 2001/20/EC Article 2 based on the principles of ICH GCP apply to this trial.

Table 1: Adverse Event Definitions

Adverse Event (AE)	Any untoward medical occurrence in a patient or clinical trial						
	participant administered a medicinal product and which does						
	not necessarily have a causal relationship with this product.						
Adverse Reaction (AR)	Any untoward and unintended response to an investigational						
	medicinal product related to any dose administered						
Unexpected Adverse Reaction	An adverse reaction, the nature or severity of which is not						
(UAR)	consistent with the applicable product information (eg						
	Investigator's Brochure for an unauthorised product or summary						
	of product characteristics (SPC) for an authorised product.						
Serious Adverse Event (SAE) or	Any AE or AR that at any dose:						
Serious Adverse Reaction (SAR)	results in death						
	 is life threatening* 						
	 requires hospitalisation or prolongs existing 						
	hospitalisation**						
	• results in persistent or significant disability or incapacity						
	• is a congenital anomaly or birth defect						
	• or is another important medical condition***						

* the term life threatening here refers to an event in which the patient is at risk of death at the time of the event; it does not refer to an event that might hypothetically cause death if it was more severe (eg a silent myocardial infarction)

** Hospitalisation is defined as an in-patient admission, regardless of length of stay, even if the hospitalisation is a precautionary measure for continued observation. Hospitalisation for pre-existing conditions (including elective procedures that have not worsened) do not constitute an SAE

*** Medical judgement should be exercised in deciding whether an AE or AR is serious in other situations. Important AEs or ARs that may not be immediately life threatening or result in death or hospitalisation, but may seriously jeopardise the participant by requiring intervention to prevent one of the other outcomes listed in the table (eg a secondary malignancy, an allergic bronchospasm requiring intensive emergency treatment, seizures or blood dyscrasias that do not require hospitalisation, or development of drug dependency).

Adverse events include:

- an exacerbation of a pre-existing illness
- an increase in the frequency or intensity of a pre-existing episodic event or condition
- a condition (regardless of whether PRESENT prior to the start of the trial) that is DETECTED after trial drug administration. (This does not include pre-existing conditions recorded as such at baseline – as they are not detected after trial drug administration.)
- continuous persistent disease or a symptom present at baseline that worsens following administration of the trial treatment

Adverse events do NOT include:

 Medical or surgical procedures: the condition that leads to the procedure is the adverse event

- Pre-existing disease or a condition present before treatment that does not worsen
- Hospitalisation where no untoward or unintended response has occurred eg elective cosmetic surgery
- Overdose of medication without signs or symptoms

6.1.3.2 Other Notifiable Adverse Events

Adverse events inconsistent with the known effects of study medication will be reported via the yellow card system ⁽⁸⁷⁾ at the judgement of the study physician and CI.

6.11.3.3 Procedures to follow in the event of female participants becoming pregnant: Not Applicable.

6.11.3.4 Investigator responsibilities relating to safety reporting:

All non-serious AEs and ARs, whether expected or not, should be recorded in the patient's medical notes and reported in the toxicity (symptoms) section of the Follow-up Form and sent to UCL CTU within 7 days. It is the responsibility of the study physician and CI to use clinical judgement regarding the discontinuation of treatment due to adverse events.

